## 2.3 BENEFIT - RISK ASSESSMENT

The favourable benefit-risk ratio based on the so far acquired knowledge about nintedanib is the rationale to conduct further studies with nintedanib in idiopathic pulmonary fibrosis.

As described in [Section 1](#), patients with IPF, including patients with only limited FVC impairment, may benefit from lesser decline in lung function and hence slower disease progression as a result of treatment with nintedanib [\[P15-09946\]](#). In addition, nintedanib significantly reduced the risk of first acute exacerbation in 2 out of 3 clinical trials [\[P11-11216, P14-07514\]](#).

Two thirds of the patients in this trial will be treated with placebo for the first 12 weeks of the trial. A 1:2 randomization (nintedanib:placebo) increases the number of patients treated with placebo during the first 12 weeks and consequently increases the power of assessing the association between change in the extracellular matrix (ECM) biomarker CRPM over 12 weeks and disease progression in placebo treated patients. Change in the extracellular matrix (ECM) biomarker CRPM over 12 weeks will be classified as stable or falling [ $\leq 0$  ng/ml/month] or rising [ $> 0$  ng/ml/month] in line with the PROFILE cohort [R15-1220]. A 12 week placebo period is considered acceptable given that the in- and exclusion criteria assure inclusion of patients with mostly preserved lung function at baseline. In addition, it is unclear if patients would even receive antifibrotic treatment as in clinical practice. IPF patients with limited lung function impairment might not be reimbursed in some countries depending on a FVC % predicted threshold (e.g.  $>80\%$  predicted).

Following the 12 week placebo controlled period all patients in this trial will continue further treatment with nintedanib. This will allow active treatment also to patients previously on placebo. In the subgroup of patients by baseline FVC ( $>80\%$  versus  $\leq 80\%$  predicted) in the pooled INPULSIS data set, the risk of disease progression (time to FVC decline  $>10\%$  or death) up to 12 weeks was low and similar in patients treated with placebo and nintedanib (approximately 10% of patients, respectively), although there was a risk reduction in favour of nintedanib by approx. 40% in the end of the 52 week treatment period for both subgroups and a consistent effect on reducing the annual rate of decline by 50%, similar to the primary outcome in the overall population [P15-09946].

The risks of treatment with nintedanib are described in [Section 1.2](#). The most common side effects of nintedanib are of gastrointestinal nature (diarrhea, nausea, vomiting, abdominal pain), as well as liver enzyme elevations.

Safety monitoring in this trial will consist of regular visits to the investigational site, timely blood analyses and specific monitoring procedures to follow-up potential hepatic enzyme elevation (potential for drug-induced liver injury), see also [Section 5.3.6.1](#).

In case of lack of tolerability, symptomatic treatment, dose adjustments and/or interruptions of trial drugs (at the discretion of the investigator) should be considered to allow for resolution of the symptoms ([Section 4.2.1](#)).

Based on the mode of action of nintedanib, especially on the inhibition of VEGF or VEGF receptors, arterial hypertension, gastrointestinal perforations, thromboembolism and bleeding have been identified as potential risks of nintedanib treatment. Therefore, patients requiring full dose concomitant anticoagulation, fibrinolysis or high-dose antiplatelet therapy will be excluded from this trial.

The mode of action of nintedanib indicates a high potential for teratogenicity and/or embryotoxicity, including fetotoxicity/lethality. In women of childbearing potential receiving nintedanib, contraceptive measures must be employed 28 days before treatment initiation, during the treatment and for a period of 3 months after last drug intake.

Overall, the clinical safety profile of nintedanib as established during the development programs including patients with less advanced disease is interpreted as favourable for the intended indication of IPF.

### 3. DESCRIPTION OF DESIGN AND TRIAL POPULATION

#### 3.1 OVERALL TRIAL DESIGN AND PLAN

This is a multi-centre, multinational, prospective trial. The trial comprises two periods. The first period is a 12 week, randomised, double blind, placebo controlled, parallel group period to assess the effect of nintedanib 150 mg bid on change of ECM biomarker turnover indicative of disease progression compared to placebo. The second period is a single arm, open label, active treatment period (nintedanib 150 mg bid) of 40 weeks duration. The total treatment period duration is 52 weeks. (Table 3.1:1).

Table 3.1:1 Summary of treatments

	Number of patients per treatment arm	Treatment period	
		Period 1	Period 2
		12 week, randomised, double blind, placebo controlled, parallel group	40 week, single arm, open label, active treatment period
Treatment	~117	nintedanib 150 mg bid*	nintedanib 150 mg bid*
Treatment	~233	placebo matching nintedanib 150 mg bid*	nintedanib 150 mg bid*
Total number of patients	~350		

\*Permanent or intermittent dose reduction to a total daily dose of nintedanib 200 mg as well as subsequent re-escalation are allowed, further details are described in [Section 4.2.1](#).

The overall trial scheme is presented in Figure 3.1:1.

[figure not shown]

Figure 3.1:1 Trial scheme

After signing the informed consent (prior to any trial related procedures including any medication washout), the HRCT scan and surgical lung biopsy sample (later if available) will be sent for central review. Screening visit (Visit 1) should only be performed after the diagnosis of IPF has been confirmed by the central review. The screening period, i.e. period between Visit 1 and 2 should last from 14 days (2 weeks) to a maximum of 28 days (4 weeks).

Patients whose central lab results are available and who meet all inclusion and none of the exclusion criteria may be randomised into the 12-week, double-blind treatment period in which they will be receiving either of two possible treatments: nintedanib of total daily dose 300 mg administered twice daily, 150 mg in the morning and 150 mg in the evening or equivalent placebo bid in double-blind fashion. The chance of receiving either of the above mentioned treatments will be 1 (active treatment): 2 (placebo). Randomisation will be performed using an Interactive Response Technology System (IRT). Following the randomised, double blind, placebo controlled treatment period, all patients will enter the single arm, open label, active treatment period of 40 weeks. All patients previously receiving placebo will start taking nintedanib. During the trial patients will be returning to the clinic for the visits as per [Flow Chart](#) for the assessment of efficacy and safety parameters as well as assessment of compliance with the study drug.

Dose adjustment visits may occur at any time to manage adverse events. Permanent or intermittent dose reduction to a total daily dose of nintedanib 200 mg, i.e. 100 mg bid and drug interruptions are allowed to manage AEs as described in [Section 4.2.1](#). Re-escalation to nintedanib 150 mg bid is allowed as described in [Section 4.2.1](#). Each time a dose reduction or re-escalation is made, the patient must return for an unscheduled visit.

Upon completion of the 52 week treatment period (12 weeks Part 1 and 40 weeks Part 2), patients will enter a 28 day (4 week) Follow-Up period. Each patient will attend a total of 12 scheduled visits (Visit 0 and Visits 1 to 11 scheduled as per [Flow Chart](#)). Patients, who prematurely and permanently discontinue study treatment prior to 52 weeks, will be asked to return to the clinic and attend all visits as originally planned per protocol [Flow Chart](#).

Each patient's participation in the trial is estimated to last a total of approximately 58 weeks.

Depending on patient's informed consent, a blood sample for pharmacogenetics should be drawn at Visit 2 or at any subsequent visit from any randomised patients who received at least one dose of trial medication.

For an overview plan of procedures please refer to the [Flow Chart](#) at the beginning of this protocol.

Adverse events will be collected, documented and reported from the time the patient signs an Informed Consent up until 28 days after the last dose of study medication.

### 3.1.1 Administrative structure of the trial

The sponsor of this trial is Boehringer Ingelheim (BI). Clinical trial drug supplies, i.e. trial medication will be provided by the sponsor.

Boehringer Ingelheim has appointed the Trial Clinical Monitor, responsible for coordinating all required activities, in order to

- manage the trial in accordance with applicable regulations and internal SOPs,
- direct the clinical trial team in the preparation, conduct, and reporting of the trial,
- ensure appropriate training and information to Local Clinical Monitors (CML), Clinical Research Associates (CRAs), and Investigators of participating countries.

Data Management and Statistical Evaluation will be done by BI according to BI SOPs.

Tasks and functions assigned in order to organise, manage, and evaluate the trial will be defined according to BI SOPs. A list of responsible persons and relevant local information can be found in the ISF.

A Coordinating Investigator has been nominated and will be responsible to coordinate investigators at different centres participating in this multicentre trial. The Coordinating investigator was selected by the sponsor.      will review the trial protocol, any subsequent amendments to the protocol and the (draft) Clinical Trial Report (CTR).      will provide signature on the final protocol signature page and amendments and will provide      signature on the CTR indicating that, to the best of the co-ordinator's knowledge, the final CTR accurately describes the conduct and results of the trial.

Sites selected for participation will consist of centres experienced in the treatment and management of IPF.

The following local facilities/equipment along with the medically needed equipment to routinely treat patients are required at the trial site:

- equipment for measuring body height
- scales for measuring patient weight
- sphygmomanometer (blood pressure instrument)
- 12-lead ECG device
- refrigerator
- freezer (-20°C)
- laboratory tabletop centrifuge (ambient)
- equipment for DLCO measurements (or availability to perform measurements if not available directly at the site)
- device for pulse oximetry measurement
- premises for performing PFTs, blood and/or urine sampling and handling of samples (PK/PD/PG/ biomarker and or safety)
- weather station (to measure atmospheric temperature, barometric pressure and humidity), all parameters will be needed for spirometer calibration

- internet access
- analogue fax line

CROs:

- CRO for provision of in clinic spirometers and home spirometry devices.
- CRO/s for HRCT and surgical lung biopsy reviews
- CRO for central laboratory for safety laboratory, biomarkers, PK and pharmacogenetic sampling logistics.
- CROs for provision of CRAs.

IRT: An IRT (IVRS/IWRS, ie Interactive Voice/Web Response System) will be used for randomisation in this trial and for appropriate re-supply and assignments of trial medication to patients during treatment period. The ability to unblind will be available via the IRT.

Relevant documentation on the participating (Principal) Investigators and other important participants will be filed in the trial master file (TMF) in accordance with BI SOPs

### 3.2 DISCUSSION OF TRIAL DESIGN, INCLUDING THE CHOICE OF CONTROL GROUP(S)

Patients with idiopathic pulmonary fibrosis having a FVC of at least 80% of the predicted normal value at baseline will be eligible for participation in this trial. It is considered acceptable in this patient population to include a 12 week placebo-controlled treatment phase (refer to [Section 2.3](#)) in order to compare the effect of nintedanib versus placebo on change in ECM biomarker turnover.

In the PROFILE study [[R15-1220](#)], these biomarkers have shown their predictive potential for disease progression as early as after the period of 3 months.

A 1:2 randomisation (nintedanib:placebo) increases the number of patients treated with placebo during the first 12 weeks and consequently increases the power of assessing the association between change in the extracellular matrix (ECM) biomarker CRPM over 12 weeks and disease progression in placebo treated patients. Change in the extracellular matrix (ECM) biomarker CRPM over 12 weeks will be classified as stable or falling [ $\leq 0$  ng/ml/month] or rising [ $> 0$  ng/ml/month] in line with the PROFILE cohort [[R15-1220](#)].

Fibrotic remodelling of the lung interstitial tissue with subsequent restrictive ventilatory defect represents the core element of the histopathology of IPF. Therefore, FVC decline is considered a marker of disease progression and will be assessed via supervised spirometry at regular clinic visits as well as via home spirometry. Home spirometry may allow a more sensitive estimate of lung function decline based on more points of measurement resulting in higher accuracy and/or less variability in calculating the slope. Consequently, this study will also provide the opportunity to compare changes in FVC over the course of the study using standard clinic spirometry compared to home measurements, i.e. generate data on the general feasibility and validity of home spirometry in IPF.

After 12 weeks of double-blind treatment, all patients will enter the 40 week single active arm phase of the trial to potentially benefit from nintedanib treatment. Total treatment duration of 52 weeks is considered adequate to assess disease progression and the predictive value of ECM biomarker turnover in this patient population.

The most frequent symptoms in patients with IPF are dyspnoea and cough. These symptoms substantially reduce the quality of life and cause major restriction in everyday life, as well as incapacity in many patients with IPF. Therefore, a number of patient-reported outcome instruments (questionnaires) will be used to document the effect of nintedanib on symptoms (shortness of breath) and patient's health related quality of life.

The frequency of visits will allow close monitoring of adverse events, as well as control of liver enzyme values, consistent with the recommendations of the prescribing information for nintedanib.

### **3.3 SELECTION OF TRIAL POPULATION**

Participation in this trial will be available to patients with IPF who meet the eligibility requirements specified in this protocol.

Recruitment will be competitive. The patients will be recruited from approximately 100 trial sites. Additional sites may be initiated to ensure trial recruitment as well as sponsor timelines.

Every effort should be made to keep patients in the study until completion of all study related procedures described in the clinical trial protocol.

A log of all patients enrolled into the trial (i.e. who have signed informed consent) will be maintained in the ISF at the investigational site irrespective of whether they have been treated with investigational drug or not.

#### **3.3.1 Main diagnosis for trial entry**

Any patients with confirmed diagnosis of IPF and who comply with eligibility requirements may qualify for participation in the trial.

Please refer to [Section 8.3.1](#) (Source Documents) for the documentation requirements pertaining to the in- and exclusion criteria.

#### **3.3.2 Inclusion criteria**

1. Written informed consent consistent with ICH-GCP and local laws, signed prior to participation in the trial including any study related procedures being performed [including any required washout as well as sending HRCT and lung biopsies (the latter if available)];

2. Male or female patients aged  $\geq 40$  years at Visit 1;
3. A clinical diagnosis of IPF within the last 3 years from Visit 0, based upon the ATS/ERS/JRS/ALAT 2011 guideline ([P11-07084](#));
4. Chest high resolution computed tomography (HRCT) scan performed within 18 months of Visit 0;
5. Combination of HRCT pattern and surgical lung biopsy pattern (the latter if available) as assessed by central review are consistent with the diagnosis of IPF ([Appendix 10.1](#));
6. FVC  $\geq 80\%$  of predicted normal at visit 1. NOTE: If this is not achieved at the screening visit, the visit may be repeated once within two weeks.

### 3.3.3 Exclusion criteria

1. ALT, AST  $> 1.5$  fold upper limit of normal (ULN) at Visit 1;
2. Total bilirubin  $> 1.5$  fold ULN at Visit 1;
3. Patients with underlying *chronic* liver disease (Child Pugh A, B or C hepatic impairment);
4. Relevant airways obstruction [i.e. pre-bronchodilator FEV1/FVC  $< 0.70$  (i.e. 70%) at Visit 1];
5. History of myocardial infarction within 6 months of visit 1 or unstable angina within 1 month of Visit 1;
6. Bleeding Risk:
  - Known genetic predisposition to bleeding;
  - Patients who require fibrinolysis, full-dose therapeutic anticoagulation (e.g. vitamin K antagonists, direct thrombin inhibitors, heparin, hirudin etc.) or high dose antiplatelet therapy;
  - History of haemorrhagic central nervous system (CNS) event within 12 months prior to Visit 1;
  - History of haemoptysis or haematuria, active gastro-intestinal bleeding or ulcers and/or major injury or surgery within 3 months prior to Visit 1;
  - International normalised ratio (INR)  $> 2$  at Visit 1;
  - Prothrombin time (PT) and partial thromboplastin time (PTT)  $> 150\%$  of ULN at Visit 1;
7. Planned major surgery during the trial participation, including lung transplantation, major abdominal or major intestinal surgery;
8. History of thrombotic event (including stroke and transient ischemic attack) within 12 months of Visit 1;

9. Creatinine clearance < 30 mL/min calculated by Cockcroft–Gault formula at Visit 1 ([Appendix 10.2](#));
10. Treatment with nintedanib, pirfenidone, azathioprine, cyclophosphamide, cyclosporine, any other investigational drug, n-acetylcysteine, prednisone/prednisolone >15 mg daily or >30 mg every 2 days OR use of other systemic corticosteroids as well as any investigational drugs within 4 weeks of Visit 2;
11. Known hypersensitivity to nintedanib, peanut, soya or to any other components of the study medication;
12. Prior discontinuation of nintedanib treatment due to intolerability/ adverse events considered drug related;
13. A disease or condition which in the opinion of the investigator may interfere with testing procedures or put the patient at risk when participating in this trial;
14. Alcohol or drug abuse which in the opinion of the treating physician would interfere with the treatment and would affect patient's ability to participate in this trial;
15. Patients not able to understand and follow any study procedures such as but not limited to home spirometry, including completion of self-administered questionnaires without help;
16. Women who are pregnant, nursing, who plan to become pregnant while in the trial or female patients with positive pregnancy ( $\beta$ -HCG) test at Visit 1 and/or Visit 2;
17. Women of childbearing potential not willing or able to use highly effective methods of birth control per ICH M3 (R2) that result in a low failure rate of less than 1% per year when used consistently and correctly.  
**NOTE: In women of childbearing potential receiving nintedanib, contraceptive measures must be employed 28 days before treatment initiation, during the treatment and for a period of 3 months after last drug intake;**
18. Patients with acute IPF exacerbation or any respiratory tract infection in the four weeks prior to Visit 1 or during the screening period.  
Visit 1 and/or Visit 2 should be postponed in case of an IPF exacerbation or respiratory tract infection. Refer to [Section 6.1](#) for information on re-scheduling of visits;
19. Patients who are or have been participating in another trial with investigational

drug/s within one month prior to Visit 1 and patients who have previously been enrolled in this trial.

Laboratory parameters found abnormal at visit 1 may be re-tested once prior to Visit 2.

Exceptions: prophylactic low dose heparin or heparin flush as needed for maintenance of an indwelling intravenous device (e.g., enoxaparin 4000 IU s.c. per day) and prophylactic use of antiplatelet therapy (e.g., acetyl salicylic acid up to 325 mg/d, **and/or** clopidogrel at 75 mg/d, **and/or** equivalent doses of other antiplatelet therapy).

Definition of major is per investigator judgement.

Women of childbearing potential are defined as: Any female who has experienced menarche and does not meet the criteria for "women not of childbearing potential" defined as: Women who are postmenopausal (12 months with no menses without an alternative medical cause) or who are permanently sterilised (e.g., tubal occlusion, hysterectomy, bilateral oophorectomy or bilateral salpingectomy).

A list of contraception methods meeting these criteria is provided in the patient information.

Patient will need to perform at least one home spirometry manoeuvre between Visit 1 and Visit 2 (in order to obtain baseline PFT values) to be eligible for the trial.

### 3.3.4 Removal of patients from therapy or assessments

#### 3.3.4.1 Removal of individual patients

An individual patient is to be withdrawn from trial treatment if:

- The patient withdraws consent for study treatment or study participation, without the need to justify the decision;
- The patient needs to take concomitant drugs that interfere with the investigational product ([Section 4.2.2](#));
- The patient can no longer be treated with trial medication for other medical reasons (such as surgery, adverse events, other diseases, or pregnancy);  
If a patient becomes pregnant or pregnancy is suspected during the trial, the patient will be permanently discontinued from the study treatment and will be followed up until birth or otherwise termination of pregnancy, please see [Section 5.3.7](#).
- The patient experiences signs and symptoms of acute myocardial ischemia or stroke;
- The patient experiences hepatic injury defined as follows:
  - ALT and/or AST  $\geq$  8 fold ULN
  - ALT and/or AST  $\geq$  3 fold ULN and total bilirubin  $>$ 2 fold ULN
  - ALT and/or AST  $\geq$  3 fold ULN and unexplained INR  $>$  1.5

- ALT and/or AST  $\geq$  3 fold ULN and unexplained eosinophilia ( $>$  5%)
- ALT and/or AST  $\geq$  3 fold ULN and appearance of fatigue, nausea, vomiting, right upper abdominal quadrant pain and tenderness, fever and/or rash.
- For potential drug induced liver injury (DILI) follow up requirements please see [Sections 4.2.1.3](#) and [5.3.6.1](#).
- The patient experiences unacceptable toxicity despite dose adjustments and supportive care
- Gastrointestinal perforation;
- Major surgery including abdominal or intestinal surgery;
- Signs or symptoms of acute myocardial ischemia, stroke, deep vein thrombosis and pulmonary embolism

In addition, permanent discontinuation of nintedanib should be considered in the following situations:

- Patients who require full dose therapeutic anticoagulation or high dose antiplatelet therapy;
- Increased risk of bleeding (e.g. gross/ frank haemoptysis or haematuria, active gastro-intestinal bleeding or ulcers).

In such cases, continuation of nintedanib should be discussed with the patient and the decision based on an individual benefit-risk assessment documented in the source data.

If a patient permanently discontinues a study drug, he/she will undergo procedures for early treatment discontinuation and will be invited to attend all planned study visits until week 56 as outlined in the [flow chart](#).

For all patients the reason for withdrawal (e.g. adverse events) must be recorded in the (e)CRF. These data will be included in the trial database and reported.

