#### 4.2.2 Restrictions

##### 4.2.2.1 Restrictions regarding concomitant treatment

Concomitant medications (or therapy) to provide adequate care may be given as clinically necessary. If restricted concomitant therapy is necessary treatment with study medication should be permanently discontinued (except in case of acute IPF exacerbations – refer to [Section 4.2.1.1](#)).

Table 4.2.2.1: 1 Permitted and Restricted Concomitant therapy

	Prior to randomisation	During treatment period	After EOT (Follow-up Period)	After early EOT 
Nintedanib	Not permitted in the 4 weeks prior to visit 2 	Study medication	Permitted	Permitted 
Pirfenidone, N-acetylcysteine, Azathioprine, Cyclophosphamide, Cyclosporine	Not permitted in the 4 weeks prior to visit 2 	Not permitted	Not permitted	Permitted
Prednisone/ Prednisolone and/or other systemic corticosteroid 	Not permitted in the 4 weeks prior to visit 2 	Not permitted	Not permitted	Permitted
Investigational Medication	Not permitted in the 4 weeks prior to visit 2 	Not permitted	Not permitted	Not permitted
Anticoagulation at full dose  , antiplatelet therapy at high dose  , fibrinolysis	Permitted	Not permitted	Not permitted	Permitted

1. Washout should not occur before the patient has signed informed consent
2. Prednisone/ Prednisolone >15 mg daily or >30 mg every 2 days OR use of other systemic corticosteroids within 4 weeks of visit 2.
3. Anticoagulation at full dose (vitamin K antagonists, direct thrombin inhibitors, heparin, hirudin, etc). Exceptions: prophylactic low dose heparin or heparin flush as needed for maintenance of an indwelling intravenous device (e.g. enoxaparin 4000 I.U s.c per day)
4. Antiplatelet therapy at high dose. Exceptions: prophylactic use of antiplatelet therapy (e.g. acetylsalicylic acid up to 325 mg/day and/or clopidrogrel at 75 mg/day and/or equivalent doses of other antiplatelet therapy) is allowed
5. For patients who withdrew study medication before the planned EOT date and decide to attend all remaining study planned visits.
6. At the discretion of the treating physician.

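### Protocol 3.3.4.1 and 4.2.2.1 disagree on whether a patient who newly needs full-dose anticoagulation or high-dose antiplatelet therapy may stay on study drug; the 3.3.4.1 hepatic stop list is also slightly narrower than 4.2.1.3 and 5.3.6.1

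*Protocol*

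**What the plan says.** Protocol 3.3.4.1 has two lists. The first gives reasons for which a patient is to be withdrawn from trial treatment. It includes needing concomitant drugs that interfere with the investigational product, with a reference to Section 4.2.2, and "Signs or symptoms of acute myocardial ischemia, stroke, deep vein thrombosis and pulmonary embolism". The second list is softer: "permanent discontinuation of nintedanib should be considered in the following situations". Its first entry is "Patients who require full dose therapeutic anticoagulation or high dose antiplatelet therapy". For these patients, "continuation of nintedanib should be discussed with the patient and the decision based on an individual benefit-risk assessment", recorded in the source data.

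Protocol 4.2.2.1 says: "If restricted concomitant therapy is necessary treatment with study medication should be permanently discontinued", "except in case of acute IPF exacerbations". Table 4.2.2.1:1 has a row for full-dose anticoagulation, high-dose antiplatelet therapy and fibrinolysis. It marks them as not permitted during treatment and in follow-up after end of treatment, and as permitted after early end of treatment. Footnote 5 describes that last column: "For patients who withdrew study medication before the planned EOT date and decide to attend all remaining study planned visits".

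On liver injury, 3.3.4.1, Table 4.2.1.3:1 (footnote 2) and 5.3.6.1 each give five criteria. The first two lists are stop rules. The third defines the adverse event of special interest and the alert.

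**The concern.** A site that reads 3.3.4.1 may keep such a patient on study drug once the benefit-risk decision is documented. A site that reads 4.2.2.1 may not. With about 100 planned sites (Protocol 3.3), the same clinical situation could be handled differently from one site to the next.

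The rule concerns a risk that the protocol itself names. Section 2.3 lists bleeding among the potential risks of nintedanib and, for that reason, excludes patients who need these drugs at entry. Section 1.2 notes that patients on full-dose anticoagulation were excluded from the INPULSIS trials. Whether such a patient may remain on nintedanib should therefore not depend on which page is consulted.

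The hepatic lists raise the same kind of question on a smaller scale: two permanent-stop lists in one protocol should not have different thresholds.

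**Working it through.** No arithmetic applies; the check is a comparison of text.

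**Step 1. Remove the situations in which the sections agree.** In acute IPF exacerbation, 4.2.2.1 makes an exception and 4.2.1.4 allows interruption for short-term full anticoagulation. Acute myocardial ischaemia, stroke, deep vein thrombosis and pulmonary embolism are mandatory withdrawals under 3.3.4.1 whatever drug is started. What remains is a new need for these drugs for any other reason. New atrial fibrillation would be one illustration, which is mine and not the protocol's.

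**Step 2. Compare the rules for what remains.**

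| | 3.3.4.1, second list | 4.2.2.1 and its table |
|---|---|---|
| Drugs | Full-dose anticoagulation, high-dose antiplatelet | The same two, plus fibrinolysis |
| Action | Consider a permanent stop | Stop permanently |
| May the patient continue? | Yes, with documented benefit-risk | No |
| Exception | Investigator and patient decision | Acute exacerbation only |

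Both sections use *should*. The difference is between stopping and considering stopping.

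**Step 3. Look for text that settles it.**
- The specific rule does not displace the general one. The 4.2.2.1 sentence is general, but its table names the same drugs as 3.3.4.1 does and carries no benefit-risk exception.
- The early-end-of-treatment column gives no latitude, because it applies only to patients already off study drug.
- 3.3.4.1 points both ways. Its mandatory list covers interfering drugs and cites 4.2.2, where these drugs are restricted; its second list then treats them as discretionary.
- 4.2.1.4 lets approved medications be started freely in significant deterioration (absolute FVC decline above 10%, DLCO above 15%). It does not say whether study drug then stops if the medication is one of these.

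None of these resolves the conflict.

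**Step 4. Compare the hepatic criteria.**

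| Criterion | 3.3.4.1 | 4.2.1.3 and 5.3.6.1 |
|---|---|---|
| ALT/AST alone | ≥8 × ULN | ≥8 × ULN |
| ALT/AST ≥3 × ULN with bilirubin | >2 × ULN | ≥2 × ULN |
| ALT/AST ≥3 × ULN with unexplained INR | >1.5 | >1.5 |
| ALT/AST ≥3 × ULN with unexplained eosinophilia | >5% | >5% |
| ALT/AST ≥3 × ULN with right upper quadrant signs | pain *and* tenderness | pain *or* tenderness |

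Three criteria match and two differ. The difference changes a decision only when ALT/AST is at least 3 but below 8 × ULN and the sole trigger is either bilirubin at exactly 2.0 × ULN or one of pain and tenderness without the other. A site using footnote 2 of Table 4.2.1.3:1 would stop permanently. A site using the 3.3.4.1 list would not, but the transaminase columns of the same table would still lead it to reduce or interrupt at 3 to <5 × ULN and to interrupt at 5 to <8 × ULN, with repeat tests at 48/72 hours.

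**Step 5. Trace it into the SAP.** Table 6.2:1 has code C5 (drug not stopped although 3.3.4.1 criteria were met) and code D1 (prohibited therapy taken). A documented continuation falls under D1. Whether it also falls under C5 depends on which list in 3.3.4.1 is applied. Both codes are set by medical review, and neither excludes a patient from any analysis set. Table 6.1:1 ends efficacy data the day after last drug intake, so a different stop decision can change which measurements enter an analysis.

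**The case against.** The strongest reply is that the sections can be reconciled. 3.3.4.1 is the dedicated removal section, it names these drugs, and it requires discussion with the patient and a documented decision. Section 1.2 reports a recommendation to treat patients at known bleeding risk only when benefit outweighs risk, so discretion may be what the sponsor intends. That is plausible, and the fix allows for it. But 4.2.2.1 and its table contain no such discretion, so the intention is not written where sites look up restricted drugs.

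A reader might infer that sites receive opposite orders. They do not: no section requires continuation, and a site that stops complies with both. A reader might also infer that the SAP would miss these patients or report them inconsistently. D1 captures them, and C5 and D1 describe different violations, so meeting one and not the other is not in itself an error.

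On the liver, it is fair to say that the gap is very small and that 3.3.4.1 already refers readers to 4.2.1.3 and 5.3.6.1 for follow-up. The text does not support the inference that a patient in the gap stays on full dose. Nor is the same-blood-draw condition in 5.3.6.1 a further conflict: it belongs to an alert definition, and the stop lists need not repeat it.

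**Conclusion.** The point stands as a drafting inconsistency in a safety rule. For a new need outside acute exacerbation and outside the event-based withdrawals, one section allows continuation and the other does not, and 3.3.4.1 is not consistent within itself. The hepatic mismatch is real but secondary.

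This rests on reading restricted therapy in 4.2.2.1 as the drugs that its table marks as not permitted during treatment. The frequency cannot be estimated, since the documents give no rate of new need in the situations that remain. The rule covers all of the roughly 350 randomised patients, but that figure says nothing about how often the conflict would arise.

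It would be tempting to read this as a threat to the trial's results. The documents do not support that. Sample size and power do not depend on it, and no patient leaves an analysis set. The only route to the estimates is the on-treatment data cut-off; that effect cannot be sized and is likely small. The case for acting is patient safety and uniform conduct across sites.

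**What to change.** 1. By default, move the anticoagulation and antiplatelet item in 3.3.4.1 to the mandatory withdrawal list, with the acute-exacerbation exception of 4.2.2.1. If discretion is intended, leave 3.3.4.1 as it is for these drugs and write the documented benefit-risk exception into 4.2.2.1 and Table 4.2.2.1:1. Either way, state whether the significant-deterioration allowance in 4.2.1.4 alters the rule.
2. In the 3.3.4.1 hepatic list, change bilirubin to ≥2 × ULN and the symptom criterion to pain *or* tenderness.

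No separate SAP edit is needed, because C5 refers to 3.3.4.1 and follows whatever that section says. The cost is a few lines of protocol text, with no added patients, visits or data.
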